## 11. OTHER TRIAL ASSESSMENTS

Other trial assessments will be performed as indicated in Appendix B.

## 11.1. Medical History

Relevant and significant new medical/surgical history since completion of HOPE-2 trial participation will be confirmed at screening.

Medical histories will also be assessed for upper body functionality (i.e., PUL 2.0) and Left Ventricular Ejection Fraction (i.e., cardiac MRI). The assessment periods will cover the time from the end of HOPE-2 to the beginning of HOPE-2-OLE.

### 11.2. Pre-Treatment Medications

All medications taken prior to each infusion as part of the pre-treatment regimen (see Section 9.7) will be captured.

For each medication, generic name, indication, dose, frequency, route, and starting and stopping dates/times (if applicable) will be collected. The trade name of the medication is to be reported for combination therapies (e.g., Alka-Seltzer, Advair, etc.).

All efforts should be made to maintain the same DMD medication regimen throughout the course of the trial. This should be discussed with the subject's primary medical doctor and caregivers at the outset of the trial and during the trial follow-up period.

## 12. ASSESSMENT OF EFFICACY

Site personnel must complete trial-specific training prior to conducting trial efficacy assessments. Standardization and consistency are essential. All efforts must be made to have the same clinical evaluators conduct the PUL 2.0 for a subject throughout the duration of a trial. Additional details regarding training requirements can be found in the trial's Manual of Operations.

## 12.1. Performance of Upper Limb

The Performance of Upper Limb (PUL) was designed specifically for assessing upper limb function in ambulant and non-ambulant DMD patients (Pane et al., 2014). All the tasks included in the PUL were selected to address patient prioritized activities of daily living that are typical regardless of age, including preschool children. The PUL includes an entry item to define the starting functional testing level for a subject. The remaining PUL items are divided into three regional dimensions: high-level (shoulder), mid-level (elbow), and distal-level (wrist and hand). Trial subjects will complete testing for PUL 2.0 in the same preferred arm throughout the course of the trial.

Elbow contractures will be measured in each arm of a subject prior to the start of PUL 2.0 testing at each visit that requires testing.

PUL equipment will be standardized across investigative sites and provided by Capricor. Every effort should be made to complete a subject's PUL 2.0 assessment at approximately the same time in the morning at each required visit. In addition, each subject should be assigned a single evaluator for testing. Additional details regarding the PUL 2.0 requirements can be found in the trial's Manual of Operations and Clinical Evaluator Binder.

Patients will undergo PUL 2.0 assessment at Day 1, Months 3, 6, 9, 12 ( $\pm$ 14 days, each), 15, 18, 21, 24, 27, 30, 33, 36, 39, 42, 45, 48, 51, 54, 57, and 60 ( $\pm$ 21 days, each). All attempts will be made to perform PUL 2.0 assessment at the specified visits. In the event a subject cannot complete the entire PUL 2.0 assessment, it should be marked as not done. For example, if a patient has a broken arm, the entire PUL 2.0 assessment should not be completed until such time that the broken arm resolves.

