## 6.2. Trial Endpoints

### 6.2.1. Primary Endpoints

The *primary safety endpoint* is the incidence and severity of all treatment-emergent adverse events from baseline through Month 12.

The *primary efficacy endpoint* is change from baseline at the Month 12 timepoint in functional capacity as assessed by the full PUL 2.0 (high-level + mid-level + distal level dimensions).

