#### 13.5.2. Missing Data

There are no plans for imputation of missing data, except to linearly impute missing item scores from the PUL 2.0, when those item scores are observed before and after the missing visit, and at least 50% of the other items in the PUL 2.0 total score are non-missing. The reasons for missing data will be documented. Sensitivity analyses, however, may be performed using various assumptions for missing data to assess the impact on summary results.

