# 4.4 Handling of Dropouts or Missing Data

Subject-level listings will present data as reported. Missing or partially missing dates that are required for date-dependent definitions (e.g., TEAEs, concomitant medications) will be assumed to be the most conservative date possible.

An adverse event (AE) with a completely missing start date will be considered treatmentemergent; similarly, an AE that started the same month and year as IP administration, but with a missing start day, will be considered treatment-emergent.

When the PUL 2.0 Combined Total Score [high-level (shoulder) + mid-level (elbow) + distal level (wrist and hand] is calculated, there are subjects who cannot do the High-Level Shoulder regional assessment due to incapacity. In cases where sites left this subcategory blank rather than entering a 0, a 0 will be entered for analysis to permit calculation of the total. It should be noted that a higher score indicates higher functioning thus allowing a 0 for calculation purposes still reflects the overall incapacity of the subject.

Modest imputation of missing data is planned when modelling; this is to linearly impute missing item scores from the PUL 2.0, when those item scores are observed before and after the missing visit.

Medical history with missing stop dates will be considered ongoing. Medications with missing stop dates will be considered as concurrent use during the study and will be counted in the summary table of concomitant medications unless the start date is after the last IP administration.

Data from any subject who early terminates (ET) will be treated as follows:

• Map ET data to a scheduled visit according to the protocol defined windows (See Appendix A Section 9.1)

• If the ET data does not fall in any visit window, the ET data will be considered to have been collected at an unscheduled visit and excluded from analysis and summary tables.

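### Protocol 12.1 does not limit its not-done rule to temporary, non-DMD reasons, so disease-related inability can become a missing PUL 2.0 instead of a low one, in conflict with SAP 4.4 and Protocol 13.5.2

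*Protocol*

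**What the plan says.** The primary efficacy endpoint in Protocol 6.2.1 is "change from baseline at the Month 12 timepoint in functional capacity as assessed by the full PUL 2.0". Four rules decide what value a subject has when he cannot do all of the test.

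- **Protocol 12.1, recording.** "In the event a subject cannot complete the entire PUL 2.0 assessment, it should be marked as not done". The example that follows is an injury: "if a patient has a broken arm, the entire PUL 2.0 assessment should not be completed until such time that the broken arm resolves". The same section notes that "The PUL includes an entry item to define the starting functional testing level for a subject".
- **Protocol 13.5.2, imputation.** Missing items are interpolated linearly if they are observed on both sides of the visit and "at least 50% of the other items in the PUL 2.0 total score are non-missing". Reasons for missing data are to be documented, and sensitivity analyses are optional.
- **SAP 4.4, zero-fill.** It recognises that "there are subjects who cannot do the High-Level Shoulder regional assessment due to incapacity" and continues: "In cases where sites left this subcategory blank rather than entering a 0, a 0 will be entered for analysis".
- **SAP 4.4, imputation.** For modelling, "this is to linearly impute missing item scores from the PUL 2.0, when those item scores are observed before and after the missing visit". The 50% condition is absent.

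SAP section 8, which lists departures from the protocol's methods, mentions neither the zero-fill nor the dropped 50% condition.

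**The concern.** Loss of upper-limb function is what PUL 2.0 is there to measure. A recording rule that can convert that loss into a missing value makes missingness depend on the outcome, and the mean change of those still observed then looks better than the mean change of everyone. The broken arm in Protocol 12.1 is introduced as an example, so it illustrates the rule without restricting it, and nothing exempts inability caused by DMD.

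The same patient state can therefore give two values. A subject too weak for the shoulder tasks has a low total if the site keeps the form and SAP 4.4 is applied, and no total if the site follows 12.1 to the letter. With 13 subjects, one or two such records are enough to move the primary summary. The mid-level and distal scores, which are secondary endpoints, are exposed in the same way.

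**Working it through.** The plan states no figure on this point, so there is none to reproduce. Three checks were made.

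**1. The rules applied to three records**

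| Record | Protocol 12.1, literal | Other rule |
|---|---|---|
| A. Too weak for shoulder tasks; elbow and wrist could be scored | Whole visit not done, no total | SAP 4.4: shoulder = 0, total is low |
| B. Tires and misses a few items | Whole visit not done, completed items not kept | Protocol 13.5.2: interpolate the few items |
| C. Broken arm | Not done | No conflict |

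Only C gives the same answer whichever rule is followed. If the inability in A were at mid-level or distal level, no zero rule would exist in either document.

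**2. Can the protocol's item imputation act?**

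With J items and m missing at a visit, the share of the other items that are non-missing is (J − m)/(J − 1), and it must reach 0.50. The documents do not give J, so 10 to 30 was assumed.

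- Visit marked not done: m = J, so the share is 0/(J − 1) = 0 for every J. The condition fails.
- Form kept, some items blank: the condition holds for m ≤ (J + 1)/2, that is up to 5 of 10, 10 of 20 or 15 of 30 items.

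So 13.5.2 is blocked for every visit caught by 12.1, but it can still act on items blank for other reasons. The SAP version, without the 50% condition, could interpolate a wholly missed visit if the items are scored before and after it. It cannot do so for a permanent loss, because no later score exists.

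**3. Possible size (assumptions; the documents give no SD)**

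*Worst case.* Take N = 13 (SAP 4.1), normal changes, and the k largest decliners missing. The expected three lowest of 13 standard normal values are −1.668, −1.164 and −0.850. The shift in the observed mean is SD × (sum of the k absolute values)/(13 − k). With SD = 2.0:

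- k = 1: 2.0 × 1.668/12 = 0.28
- k = 2: 2.0 × 2.832/11 = 0.51
- k = 3: 2.0 × 3.682/10 = 0.74

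The shift is proportional to the SD. At SD 1.5 it is 0.21, 0.39 and 0.55; at SD 3.0 it is 0.42, 0.77 and 1.10.

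*Simpler model.* If k missing subjects are on average D points worse than the rest, the shift is k × D/N. With N = 13 and D from 2 to 6, it is 0.15 to 0.46 for k = 1, 0.31 to 0.92 for k = 2 and 0.46 to 1.38 for k = 3.

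**The case against.** The strongest reply is that 12.1 concerns inability to be tested, not poor performance. The entry item sets the starting level for weak subjects, a failed task is itself a score, and the only example is an injury that heals. SAP 4.4 supports this: it describes sites that entered 0 or left only the shoulder part blank, so at least some partial forms were kept and totalled. Protocol 12.1 also refers to a Manual of Operations and a Clinical Evaluator Binder, which were not available for this review and may settle item scoring. The primary endpoint is summarised descriptively, and 13.5.2 requires reasons for missing data and permits sensitivity analyses.

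Much of this stands, and it rules out three stronger readings that a reader might draw.

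- *Every subject who loses function becomes missing.* Not supported: SAP 4.4 scores shoulder incapacity as 0 when the form is kept, and nothing shows that any PUL 2.0 was marked not done for weakness.
- *Item imputation can never operate.* Not supported: it fails only for visits marked not done, and the SAP version has no 50% condition.
- *A subject not tested on Day 1 has no baseline for any PUL change.* Not settled: SAP 4.3 takes the last non-missing value before first dosing, although within this trial the schedule places PUL 2.0 before dosing only on Day 1.

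What the reply does not remove is the wording. The trigger in 12.1 is any inability to complete, the SAP's zero-fill covers one blank dimension and cannot restore a form that was never completed, and optional sensitivity analyses do not say which value is right.

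**Conclusion.** The point holds as an unreconciled rule with a possible bias in favour of the product. Protocol 12.1, read literally, allows DMD-related inability to be recorded as missing. That contradicts SAP 4.4 for the shoulder dimension, leaves mid-level and distal incapacity without any zero rule, and puts every visit it catches beyond the reach of Protocol 13.5.2.

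The documents do not show that decliners have in fact been removed from the primary endpoint, and the size of any effect cannot be derived from them. The shift of 0.28 to 0.74 points is an assumed worst case: it needs normality, an SD of 2.0, and the missing subjects to be exactly the 1 to 3 largest decliners of 13. The change should be made because it is cheap and the direction of the risk is known.

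**What to change.** **Protocol 12.1.** State three cases.

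1. Mark the visit not done only when testing is prevented by a temporary reason unrelated to DMD.
2. Score 0 for a task that cannot be performed because of DMD-related loss of function, in all three dimensions, consistent with SAP 4.4 and after checking against the PUL 2.0 scoring manual.
3. If items are omitted for another reason, keep the completed items and leave the rest missing, so that 13.5.2 applies.

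**SAP 4.4.** List every PUL 2.0 already marked not done with its documented reason. Enter items that source worksheets show were completed. Where the documented reason is loss of function, score the affected items 0 in a sensitivity analysis. This should not be a retrospective change to the main analysis, because in an open-label study that judgement would be made with outcomes known.

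**SAP section 8.** State whether the 50% condition in 13.5.2 is kept, and list the zero-fill.

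**Cost.** A protocol clarification, a short SAP addition and a review of a small number of records in 13 subjects, with no new visits or procedures. The mean change may become slightly less favourable.

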## 12.2. Cardiac MRI

Subjects will undergo cardiac MRI at the Month 24, Month 36, Month 48, and Month 60 visits (or, Early Termination Visit) if they are physically capable as determined by an Investigator. All attempts will be made to perform cardiac MRI assessment at the Month 24 visit, or as soon as possible thereafter. If the cardiac MRI at Month 24 needs to be delayed, then the cardiac MRI at Month 36, Month 48, and Month 60 should also be delayed accordingly to ensure an approximate 12-month gap between the two MRIs.

Subjects that complete the cardiac MRI will have sufficient attention span, ability to maintain a breath-hold, lack significant contractures that would otherwise make lying flat difficult, and fit properly within the MRI scanner.

It is anticipated that the duration of each MRI session will be 30-45 minutes. Acquisition parameters and techniques are specified in the MRI Imaging Manual. The site-based MRI

technologists will be trained and certified in the common acquisition protocol prior to initiation of enrollment at each site. All trial images and applicable imaging data will be sent to and centrally read at an independent, central, imaging core by DMD cardiovascular MRI and imaging experts.

## 12.3. Retrospective Assessment of Upper Body Functionality and LVEF

Medical histories will be assessed for upper body functionality (i.e., PUL 2.0) and Left Ventricular Ejection Fraction (i.e., cardiac MRI). The assessment periods will cover the time from the end of HOPE-2 to the beginning of HOPE-2-OLE.

## **13. STATISTICS**

#### 13.1. General Considerations

- 1. Descriptive statistics will be used to summarize all subject baseline and outcome data collected during the trial. Continuous variables will be summarized using mean, standard deviations, medians, and ranges. Categorical variables will be summarized in frequency distributions or as rates.
- 2. Statistical analyses will be performed by validated software (e.g., SAS, IBM/SPSS, or Cytel Software).
- 3. There are no formal hypotheses or statistical tests associated with trial endpoints except as outlined in the SAP. Statistical tests will be performed, however, for informational value as part of summarizing trial results. Parametric and non-parametric tests will be used that are appropriate to the outcome measure being summarized. Reported p-values will be considered nominal and unadjusted for multiple testing.
- 4. Copies of databases used to prepare clinical report summaries will be archived to enable any statistical analyses performed to be replicated.
- 5. A full data listing will be prepared, including an electronic version in a standard computer-accessible format (e.g., SAS) at the completion of the study. Listings of data represented on the case report forms (eCRF) will be provided for all key baseline, demographic and outcome variables to facilitate further investigation of tabulated values and to allow for clinical review of safety variables.

#### 13.2. Sample Size

Up to 16 subjects who were enrolled in the HOPE-2 trial and completed the 12-month follow-up period will be enrolled in this trial.

#### 13.3. Analysis Population

Enrolled Population: The enrolled population will include all subjects who signed the informed consent form and/or given assent.

Safety Population: The safety population will be defined as all subjects who received any amount of IP. All analyses will be based on the Safety Population.

#### 13.4. Safety Analysis

#### 13.4.1. Safety Endpoints

The primary safety endpoint and other observed adverse events will be documented and reported. Adverse events will be summarized by the incidence of events by type and by the percentages (rates) of subjects with those events.

#### 13.4.2. Pre-treatment Medications

Prescription and over-the-counter pre-treatment medication use will be coded to drug class, preferred drug name, and generic/trade drug name using the World Health Organization drug

Page 56 of 78 Capricor, Inc. - Company Confidential dictionary (WHO-DD). All reported pre-treatment medications will be listed. Frequencies and percentages of subjects reporting or receiving each medication will be summarized by WHO-DD drug class and preferred name within drug class.

#### 13.4.3. Physical Examination

Observed status (e.g., normal, abnormal) and changes from baseline in body system-specific physical examination findings will be summarized by visit within each body system.

#### 13.4.4. Safety Labs and DSA

Quantitative lab values and respective changes will be summarized across visits with mean, standard deviation, minimum and maximum. Categorical lab values will be summarized with observed status (e.g., normal, abnormal) and with tables showing shift from baseline to post-baseline visits.

### 13.5. Statistical Methods

All subject baseline and study outcomes for safety will be summarized using descriptive statistics. These descriptive statistics will be appropriate to the data type involved.

#### 13.5.1. Multiplicity

There are no pre-specified test hypotheses or assignments of statistical significance to study results requiring a consideration of adjustments for multiple testing.

#### 13.5.2. Missing Data

There are no plans for imputation of missing data, except to linearly impute missing item scores from the PUL 2.0, when those item scores are observed before and after the missing visit, and at least 50% of the other items in the PUL 2.0 total score are non-missing. The reasons for missing data will be documented. Sensitivity analyses, however, may be performed using various assumptions for missing data to assess the impact on summary results.

## 13.6. Efficacy Analysis

Efficacy will be evaluated at the 3, 6, 9,12, 15, 18, 21, 24, 27, 30, 33, 36, 39, 42, 45, 48, 51, 54, 57, and 60 month follow-up visits, with changes from baseline assessed for pre-specified endpoints.

Descriptive statistics will be used to summarize changes from baseline in the PUL 2.0 scores. Additional analyses will be conducted to assess the treatment effect and potential disease modification evidence, as outlined in the SAP.

## **13.7.** Exploratory Analysis

Descriptive statistics will be used to summarize changes from baseline in the retrospective standard-of-care patient data from HOPE-2 and the beginning of HOPE-2-OLE and/or using an external comparator arm, pertaining to upper body functionality (i.e., PUL 2.0) and Left Ventricular Ejection Fraction (LVEF) (i.e., cardiac MRI).

## 14. TRIAL OVERSIGHT

#### 14.1. Data Safety Monitoring Board

To meet the trial's ethical responsibility to its subjects, an independent Data Safety Monitoring Board (DSMB) will monitor results during the trial. The board consists of physicians and biostatistician(s) appointed by Capricor, who have no formal involvement or conflict of interest with the Investigators, investigative sites, subjects, or Capricor. The DSMB will act in a senior advisory capacity to Capricor regarding data and safety matters throughout the duration of the trial. The board will meet on a periodic basis according to the DSMB charter to monitor the available information regarding safety, efficacy, and quality of trial conduct. The DSMB will communicate their recommendations directly to Capricor. The investigative sites will have no contact with the members of DSMB and no voting member of the committee may participate in the trial as an Investigator.

## **15.** SOURCE DATA AND TRIAL DOCUMENTS

#### **15.1.** Electronic Data Capture

All trial data will be entered into the EDC system. Site personnel requiring access will have their own Login/Password. Access to trial information will be based on individual roles and responsibilities. The application employs fine-grained role-based access control for data entry, viewing and reporting options. All trial data will be transmitted over an encrypted SSL (Secure Sockets Layer) connection that requires user authentication.

This application is designed to be in full compliance with the International Conference on Harmonization and Good Clinical Practices (ICH-GCP), the FDA's CFR 21 Part 11 Electronic Record and Electronic Signatures, the FDA's "Guidance: Computerized Systems Used in Clinical Trials," and Health Insurance Portability and Accountability Act (HIPAA).

EDC supports efficient data collection and management and facilitates rapid data closure. A strong advantage of web-based design is that Capricor, or designee, has immediate access to the data from all investigative sites so that queries can be generated and distributed to the sites in real-time and the frequency of missing data can be reduced.

## 15.2. Trial Monitoring

In accordance with 21 CFR 312.56, ICH- GCP, and local regulations, trial monitors will periodically complete on-site monitoring of data with a focus on safety, trial endpoints, data completion, data outliers and data integrity. Trial monitors will schedule an on-site visit with a site coordinator for an appropriate duration based on the scope of data anticipated to be collected. Prior to the visit, a confirmation letter will be sent to the investigative site, which will include a listing of which CRFs and source documents will be reviewed.

Site coordinators are to have all source documents up to date and easily accessible to a monitor.

During an on-site monitoring visit, trial monitors are to:

- Track the overall monitoring process including data collected and entered, visit schedules, and subject screening and enrollment.
- Verify and ensure compliance with the protocol according to GCP and HIPAA requirements.
- Ensure that appropriate data corrections are made, dated, explained, and initialed by the Investigator or representative.
- Assess the impact of any personnel changes on the investigative site's ability to conduct the trial.
- Verify a minimum of the following data points for all subjects: date of birth, signed informed consent, eligibility criteria, medical history, date of enrollment, serious AEs, and mortalities.
- Perform review of informed consent process and review documentation of informed consent for completeness and correctness.

- Perform on-site validation checks of recoded data by reviewing source documents to determine whether the data reported in the EDC system are complete and accurate. Source documents include medical charts, screening records and/or logs, research procedure records and/or files, and other trial related notes.
- Monitor subject safety by verifying that any AE, therapy modification, or concomitant medications are reported in accordance with the protocol.
- Determine whether all AEs, protocol deviations, and protocol violations are appropriately reported within the required time periods according to applicable regulatory requirements as outlined in the protocol and by regulatory agencies.
- Verify that any missed visits and examinations that were not performed, as well as trial withdrawals and/or dropouts are explained and clearly reported.
- Inform the site PI about any deviations from or violations of the trial protocol, GCP and/or regulatory requirements in order for appropriate actions to be taken to prevent recurrence of the deviation and/or violation.
- Inform the Investigator of any major data entry error, delays in data entry, omissions, or eligibility requirement errors.
- Verify that regulatory documentation is accurate, complete, current, and properly maintained.
- Very that PI oversight of trial conduct is documented via signature or initials and date on documentation regarding eligibility, AEs, and abnormal laboratory values.

The monitor may also inspect the investigative site's facilities to verify that proper space for study documents, equipment and investigational product is available.

A debriefing meeting with the PI, site coordinator(s), and the Monitor to review any notable findings will be scheduled toward the end of the on-site visit. The monitor will submit a written monitoring visit report to Capricor and send a follow-up letter with findings to the PI. The report and letter will include a summary of documentation reviewed by the monitor, any significant findings, AEs, protocol deviations and violations, missing regulatory documents and actions taken, to be taken or recommended to ensure compliance. The report and letter will include a list of action items. Investigative sites are expected to complete the list of actions items within 30 days of receipt.

